9. STATISTICAL CONSIDERATIONS

9.1 General Design Issues

Aim 1a: *To evaluate pain-related fear outcomes between GET Living and TPM. Hypotheses: Compared to TPM, the GET Living group will (1) have significantly less pain-related fear avoidance (adolescent, parent) at discharge, with continued gains at 3 and 6-month follow-up; Exploratory: (2) have fewer number of days to achieve pain-related fear improvement, assessed via daily diaries.*

Aim 1b: *To evaluate disability and parent responses to pain outcomes between GET Living and TPM. Hypotheses: Compared to TPM, adolescents receiving GET Living will have (1) significantly less functional disability and protective parent responses at discharge, with continued gains at 3 and 6-month follow-up; Exploratory: (2) fewer number of days to achieve decreased functional disability and protective parent responses, assessed via daily diaries; (3) significantly better adolescent joint kinetics at discharge, assessed via motion analysis; and (4) demonstrate significantly greater increases in daily physical activity levels at discharge via actigraphy. We will also examine treatment response correlates: age, pain, gender, diagnosis, and readiness to change.*

Aim 1 Analysis Plan. GET Living vs. TPM. Linear mixed effects models will be used to compare GET Living to TPM. The outcome of interest for H_{1a} will be FOPQ-C and PFOPOQ total scores. For H_{1b}, outcomes are FDI and ARCS-Protect scores. Exploratory endpoints. Daily Diary (DD): We will use a randomization test (<https://tamalkd.shinyapps.io/scda/>)⁵³ to assess the difference between baseline (BAS) to discharge (END) and BAS to 3 and 6-month follow-up (FU)^{21,54}. We will also examine at what point during treatment significant improvements occur using delayed effect lags (one effect equals 1 day) until p-value 0.05 is reached. Actigraphy: Actilife software will be used to extract data and calculate mean and peak daily activity. Published data reduction methods will be used⁴³. We will model physical activity (mean, peak) at two time points using mixed 2 (time) x 2 (group) ANOVAs. Rate of change in physical activity from BAS to END will also be examined using DD method. Biomechanical assessment: Full body joint kinematic (motion) and kinetic (force) data will be collected with a 20-camera Vicon system (Centennial, CO, USA) with 5 integrated force plates (Bertec; AMTI). Markers will be placed on each participant according to the 3D Plug In Gait model (Vicon) with data recorded and processed in Nexus 2.6.1. Participants will walk, complete the Star excursion balance test and drop jump task^{37,41}. Biomechanical variables (stride length; peak hip and knee extensor moments; peak ankle plantarflexor moment; Star excursion balance score) will be extracted using Event Analyser (Vicon) for error free data reduction. We will model biomechanical variables using mixed 2 (time) x 2 (group) ANOVAs. We will also examine treatment response correlates: age, pain, gender, diagnosis, and readiness to change.

Aim 2: To characterize feasibility of GET Living to inform implementation of a large multi-site RCT.

Hypotheses: GET Living participants will have (1) high treatment satisfaction ratings (mean score ≥ 40 of 60; reflective of satisfied or very satisfied); *Secondary:* (2) $\geq 80\%$ sessions completed on-schedule, $\leq 20\%$ attrition rate, $\geq 80\%$ adolescent and parent daily diary adherence; *Exploratory:* (3) fewer health care costs at 3 and 6-month follow-up compared to TPM.

Aim 2 Analysis Plan. Satisfaction. We will examine mean satisfaction scores. Adherence/Retention. We will examine mean parent and adolescent adherence to daily diary completion, percent of patients who dropout prior to treatment completion, and percent of sessions completed on-schedule. Health care costs. We will examine mean costs across arms at 3 and 6-month follow-up.

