9.2 Sample Size and Randomization

We chose the largest feasible study size to obtain as precise estimates as possible of improvement in adolescent disability while ensuring adequate power for the treatment difference in the improvement in adolescent pain-related fear. This gave us a starting total sample size of 74 (37 in each arm). Based on pilot data, we expect roughly 19% attrition during treatment to a total of 60 and further attrition to 58 at end of follow-up.

Power calculations were first performed using the simplified approach of paired t-tests for the change from baseline to 3 and 6-months on those with 3 and 6-months data. For this approach, we used means and standard deviations of observed changes in pilot data. We then simulated data from our analytic model using the standard deviations at each time point and standard deviations of change to calculate correlation and hence the random effect and error variances. The mixed models simulation allowed us to use more data and yielded slightly higher power estimates.

Primary Outcome: In our primary power calculation, we assumed that the improvement in adolescent pain-related fear at 3 and 6-months would be 22.4 in GET Living and 5 in TPM, a difference of 17.4, with a standard deviation for change of 21. Under this scenario we will have power of 87% with 58 (29 in each arm) at end of study. Under more conservative assumptions, we still have power of 80% with only 52 at the end of study and a treatment difference of 16.6. With a smaller standard deviation of 18.9, we will have power of 80% with 50 at end of study and a treatment difference of 15.4.

Other Outcomes: For parent pain-related fear, our estimated treatment difference at 3 and 6-months is 13 with an estimated standard deviation for change of 8.5. This would give us power close to 100% for 58 at end of study and we would still have 90% power with a treatment difference of only 8 and only 50 left at end of study.

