For adolescent disability, our estimated treatment effect at 3 and 6-months is 7 with a standard deviation for change of 11.2, yielding power based on the t-test of 65% assuming 58 at end of study. We also created 5000 simulated datasets using a mixed effects model with standard deviations of 11.2 for change and 12.6 at each time point and estimated power by the fraction of simulated datasets in which the treatment difference at 3 and 6-months was significant at level 0.05. This provided a slightly higher power estimate of 67% and an estimated power of 79% if the treatment difference is 8 (1 point larger than expected).

Treatment Assignment Procedures

After a 2-week pre-treatment baseline period, patients will be randomized to either GET Living or TPM and stratified on fear and disability scores (see **Table 6** for scoring criteria). A block

randomization strategy will be used with randomly generated blocks of 2 and 4 to assure near equal distributions across arms and minimize the probability of predicting the next assignment. A randomization spreadsheet with four strata will be created by the study biostatistician, [name] (please see **Table 5** in section 6.2.2 for fear and disability stratification).

Patients will be randomized by an un-blinded research coordinator or postdoctoral fellow. Those who are randomized to the TPM group can opt to participate in GET Living after their study assessments are complete (6.5 months after baseline). They will no longer be considered a participant of this study at that time.

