9.6 Data Analyses

Our statistician, [name], will conduct analyses. Linear mixed effects models will be used for Aim 1. We chose the largest feasible study size to obtain as precise estimates as possible of treatment difference in our primary outcome, adolescent pain-related fear. With a starting sample of 74 (37/37), we expect 58 at follow-up (18% discharge attrition, 5% at 3 and 6-month follow-up). Using GET Living pilot data (see Table 2), we used a mixed model simulation using the standard deviations at each time point and standard deviations of change to calculate correlation and hence the random effect and error variances. In our primary power calculation, we assumed that the improvement in adolescent pain-related fear at 3 and 6-months would be 22.4 in GET Living and 5 in TPM¹⁹, a difference of 17.4, with a standard deviation for change of 21. Under this scenario we will have 87% power with 58 (29 in each arm) at study end. Under more conservative assumptions, we still have power of 80% with only 52 at the end of study and a treatment difference

of 16.6. With a smaller standard deviation of 18.9, we will have power of 80% with 50 at end of study and a treatment difference of 15.4.

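### The Aim 1 mixed model does not say how baseline enters or which contrast decides; baseline adjustment could add about 0 to 8 points of disability power with the same patients

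*Combined protocol and SAP*

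**What the plan says.** Section 9.1 (Aim 1 Analysis Plan) says "Linear mixed effects models will be used to compare GET Living to TPM" and lists the outcomes: FOPQ-C and the parent fear score for Aim 1a, FDI and ARCS-Protect for Aim 1b. Section 9.6 adds only "Linear mixed effects models will be used for Aim 1". Neither section says whether baseline is a covariate or one of the responses, whether the fear and disability factors used in the randomisation are in the model, or which visit decides each hypothesis.

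Two other places bear on the contrast. The Aim 1b hypothesis in Section 9.1 expects "significantly less functional disability and protective parent responses at discharge, with continued gains at 3 and 6-month follow-up"; Aim 1a has the same timing. Section 9.2 instead counts the simulated datasets "in which the treatment difference at 3 and 6-months was significant at level 0.05".

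Section 9.2 takes change from baseline as the basis of its simplified power calculation and continues: "We then simulated data from our analytic model using the standard deviations at each time point". That analytic model is not written out anywhere. For disability (difference 7, SD of change 11.2) the t-test result is given as "yielding power based on the t-test of 65% assuming 58 at end of study". For the simulation, with SD 12.6 at each time point, the text reads: "This provided a slightly higher power estimate of 67% and an estimated power of 79% if the treatment difference is 8".

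**The concern.** A mixed model can use the baseline score in several ways, and they differ in precision. If baseline is a response with its own mean in each arm, the treatment effect is in substance a difference in change from baseline. Randomisation makes the two baseline means equal in expectation, so estimating a difference between them adds noise. Entering baseline as a covariate removes that noise.

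This matters most for disability. It is the secondary outcome, the plan puts its power at only 65% to 67%, and Section 9.2 says the sample size was chosen partly for precision on it. Leaving both the use of baseline and the contrast open also allows them to be settled after the data are seen.

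**Working it through.** **Inputs (Section 9.2).** FDI difference 7 (or 8); SD of change 11.2; SD 12.6 at each time point; 37 per arm at the start, 30 at discharge (60 in total), 29 at the end of follow-up (58 in total); significance level 0.05, taken as two-sided. Powers come from the noncentral t distribution.

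**1. The plan's t-test figures.** Two-sample t-test on change: SE = 11.2 × √(2/29) = 2.941, 56 df, power 64.8% (stated 65%). The fear figures reproduce in the same way:

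| Outcome | Difference | SD of change | N | Power | Stated |
|---|---|---|---|---|---|
| Adolescent fear | 17.4 | 21 | 58 | 87.3% | 87% |
| Adolescent fear | 16.6 | 21 | 52 | 79.8% | 80% |
| Adolescent fear | 15.4 | 18.9 | 50 | 80.6% | 80% |
| Parent fear | 8 | 8.5 | 50 | 90.3% | 90% |

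**2. Correlation implied by the two FDI SDs.** ρ = 1 − 11.2²/(2 × 12.6²) = 0.605. The residual variance is 11.2²/2 = 62.72 and the between-patient variance is 12.6² − 62.72 = 96.04.

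**3. Mixed model with a free baseline mean in each arm, one follow-up visit.** With a random intercept and the attrition above, the variance of the estimated mean change in one arm has three parts:
- explained by baseline: (1 − 0.605)² × 158.76 = 24.78, averaged over 37 patients;
- explained by discharge given baseline: the variance of a visit given baseline is 158.76 − 96.04²/158.76 = 100.66, and the covariance of two later visits given baseline is 96.04 − 58.10 = 37.94, so 37.94²/100.66 = 14.30, averaged over 30;
- remainder: 100.66 − 14.30 = 86.36, averaged over 29.

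SE² = 2 × (24.78/37 + 14.30/30 + 86.36/29) = 2 × (0.670 + 0.477 + 2.978) = 8.25, so SE = 2.872. Power is 66.8% for a difference of 7 and 78.2% for 8 (stated 67% and 79%).

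**4. Same patients and visit, adjusted for baseline.** The first part drops out: SE² = 2 × (0.477 + 2.978) = 6.91, SE = 2.629. Power is 74.4% for 7 and 84.9% for 8, a gain of 7.6 points at 7. As a check, ANCOVA on the 58 completers has residual SD 12.6 × √(1 − 0.605²) = 10.03, SE 2.635, 55 df and power 74.2%.

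**5. Sensitivity to the correlation.** Holding the SD of change at 11.2, the SD per visit is 11.2/√(2(1 − ρ)).

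| ρ | SD per visit | Free baseline | Adjusted | Gain (points) |
|---|---|---|---|---|
| 0.605 | 12.6 | 66.8% | 74.4% | 7.6 |
| 0.7 | 14.46 | 66.4% | 72.0% | 5.6 |
| 0.8 | 17.71 | 66.0% | 69.6% | 3.6 |

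**6. Sensitivity to the baseline SD.** The entry cut-off may make the baseline spread narrower than the follow-up spread. The documents give no separate baseline SD, so the values of b below are assumptions. Follow-up SD stays at 12.6 and SD of change at 11.2. The covariance is (b² + 12.6² − 11.2²)/2 and the residual SD is √(12.6² − covariance²/b²). The comparison is completer ANCOVA against the 64.8% of step 1.

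| Baseline SD b | Covariance | Residual SD | ANCOVA power | Gain (points) |
|---|---|---|---|---|
| 7 | 41.16 | 11.14 | 65.2% | 0.4 |
| 9 | 57.16 | 10.88 | 67.2% | 2.4 |
| 10 | 66.66 | 10.69 | 68.8% | 4.0 |
| 11 | 77.16 | 10.47 | 70.6% | 5.8 |

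The gain shrinks because the regression slope on baseline (covariance/b²) rises from 0.605 at SD 12.6 to 0.84 at SD 7, and a change score is already optimal at a slope of 1. Among completers at SD 12.6 the gain would be 74.2 − 64.8 = 9.4 points. The completer comparison therefore flatters adjustment slightly. The mixed-model gain of 7.6 is the relevant upper figure, because the plan intends a mixed model.

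**The case against.** The strongest objection is that 67% to 74% is a favourable case. It needs a baseline SD of 12.6, which Section 9.2 gives only as a simulation input. Entry requires an FDI of at least 13 (Section 4.1, with a clinician-referral exception), and the pilot admission mean was 24.8 (Table 1), so a narrower baseline spread is plausible. This stands, and it is why the gain is given as a range that reaches almost zero.

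The plan's model is also inferred. A baseline-adjusted model with only 50 completers gives 67.6% and 78.9%, as close to the stated figures as step 3. The plan quotes its disability power with 58 at the end, which favours the change-from-baseline reading but does not prove it.

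The closed-form figures ignore the stratified randomisation. In 10,000 simulated trials with stratified blocks of two and four (assuming a correlation of 0.4 between FOPQ-C and FDI, which the documents do not give), power was 69.1% with free baseline means and 75.5% with the covariate. The gain was 6.4 points, against 7.1 without stratification. The direction holds and the size is slightly lower.

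Some stronger readings are tempting but unsupported:
- A reader might infer that no contrast is stated at all. Section 9.2 does point to the 3- and 6-month visits. The trouble is that this could mean one visit or their average, and that it differs from the hypotheses.
- A reader might add the higher power obtainable by averaging the two follow-up visits. That is a change of estimand, not a gain from adjustment, and it depends on a 3-to-6-month correlation that the documents do not give.
- A reader might conclude that the analysis is invalid or that the primary outcome is affected. A change-from-baseline model is valid. For fear no SD per visit is given, so no gain can be calculated; its stated power of 87% ("Under this scenario we will have power of 87% with 58 (29 in each arm) at end of study") reproduces.

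**Conclusion.** The specification gap is real: Sections 9.1 and 9.6 give a model class without the use of baseline, and the hypotheses and the power section point to different times. It should be closed even if the efficiency gain turns out small.

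For disability at a single visit, baseline adjustment raises power from about 67% to about 74% on the plan's own inputs, and by about 0 to 8 points over the range examined. This rests on a random-intercept structure, the stated attrition, correlations from 0.605 to 0.8, and assumed baseline SDs from 7 up to the plan's 12.6. Using the final-analysis level of 0.0492 (Section 9.4) changes little: the completer figures become 64.5% and 74.0%. No gain is quantified for the fear outcomes or for including the randomisation factors. The benefit concerns one secondary outcome of a trial that calls itself exploratory, so this is a recommended improvement and not a fault that threatens validity.

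**What to change.** In Sections 9.1 and 9.6:

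- Name one target contrast for each Aim 1 outcome (discharge, one follow-up visit, or the average of the two follow-up visits), and make the hypothesis and the power section agree with it.
- Analyse the post-baseline visits as responses, with that outcome's baseline score as a continuous covariate. Include baseline FOPQ-C and FDI in every model, because they are the randomisation factors.
- In Section 9.2, restate disability power for that model and contrast, and show how it depends on the correlation and on the baseline SD.

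The cost is SAP wording and one re-run of the power simulation. All the scores are already collected at baseline (Table 6), and no patient or visit is added.

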
biostatistician will also create a randomization scheme to determine the number of days for the pre-treatment baseline period for each individual participant (2 weeks on average).

Study Procedures. At the BAS visit participants will complete informed assent/consent, complete baseline questionnaires, begin daily diaries, and begin wearing an Actigraph. Child participants will undergo biomechanical assessment (**[name]**, Director of the Motion and Sports Performance Laboratory at SCH) during this visit. Notification of treatment arm allocation will occur at the end of the pre-treatment baseline period, and treatment will begin according to randomized group allocation: GET Living or TPM. Discharge testing occurs at the end of GET Living or TPM and includes participant questionnaires, child biomechanical assessment, and an exit interview. Daily diary and actigraphy ends at discharge. At 3 and 6 months follow-up, participants complete daily diaries for 7-days and self-report questionnaires.

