Treatment Conditions. Participants will be randomized into: **GET Living or Typical Pain Management (TPM)**. During the study, participants will be instructed to not seek new treatments for pain. **GET Living.** An outpatient team consisting of a pain psychologist and physical therapist (PT) provide GET Living, both trained in this modality of treatment by [name] with ongoing consultation from [name] (lead innovator of GET in adults) and exposed to treatment session videos from participants in the pilot. GET Living is focused and individually tailored. The primary aim of GET Living is returning to valued activities of daily life and restoring daily functioning, including return to school. The treatment manual, entitled **GET Living: Graded Exposure Treatment for children and adolescents with chronic pain** was adapted from the adult treatment manual⁴⁹ (see **Section 5.1** detailed description). The protocol consists of 12 50-minute sessions delivered twice a week for up to 12 weeks. Sessions 1-5 (education, formulation, goals) are conducted with the psychologist, PT, adolescent, and parent. Graded exposure begins in session 6. The psychologist and PT co-lead a portion of the exposure sessions. During the remaining exposure sessions, the PT leads the exposures while the pain psychologist meets individually with the parent. The final two sessions focus on relapse prevention and future goal setting. **Typical Pain Management.** After randomization, participants allocated to the TPM group will initiate treatment, as indicated by the TPM treatment manual. To ensure dose equivalency, we increased this to 6-Psychology/6-PT with 3 parent-only sessions. In pain management psychology⁵⁰ child and parent sessions focus on biopsychosocial model education, goal setting, pain coping skills training, and cognitive restructuring. PT sessions are based on Guide to Physical Therapy Practice 3.0⁵¹ consisting of 1) therapeutic exercise, 2) balance and proprioception, 3) strength training, and 4) use of modalities (e.g., heat/cold pack).

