5. STUDY INTERVENTIONS

5.1 Interventions, Administration, and Duration

GET Living: Participants randomized into the **GET Living** intervention group, will participate in 12 sessions, 1-hour each, delivered twice a week over for up to 6 weeks.

Phase I-III. The goals of Phase I-III are to educate the participants about the fear avoidance model of pain (individual and interpersonal), present the treatment rationale and formulation, create values-based treatment goals to enhance motivation, and create a pain-related fear hierarchy from the PHODA-YE results to design specific exposures. The pain psychology therapist (PSY) and PT are both present for these sessions to ensure that the treatment message is consistent from both providers to the family. Most of these activities are conducted jointly with the adolescent and parent present, although this varies with the developmental level of the adolescent. For example, while younger adolescents require parental input when developing fear hierarchies, most older adolescents do not want or need parent involvement to complete this task. In addition, depending on parent awareness of their own distress and behavior that may be impacting their adolescent's functioning, the interpersonal fear avoidance model formulation may initially be presented separately. The decision on whom to include for the different treatment exercises in these initial sessions will be jointly negotiated by the therapists, patient, and parents.

Phase IV. Graded Exposure consists of engaging in activities perceived as potentially 'harmful' or 'worrisome' in a controlled and continuous manner in order to elicit anxiety and to foster habituation and the subsequent

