9.5.4 Exploratory Outcomes

Physical Activity (Actigraphy), Daily Diary (Child and Parent), and Biomechanics (motion analysis) are exploratory outcomes. Actigraphy will be measured during 2-week pre-treatment baseline throughout active treatment. The Daily Diary will be administered for an average of 14 days during the initial baseline period through treatment, and again for 7 days at the 3 and 6-month follow-up time points. Motion analysis will be conducted at Baseline and Discharge sessions.

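### The within-patient diary randomization test has little power for slow improvement by discharge, the lag search does not repair it, and no between-arm diary analysis is stated

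*Combined protocol and SAP*

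**What the plan says.** The Aim 1 Analysis Plan in Section 9.1 uses a randomization test on the diary "to assess the difference between baseline (BAS) to discharge (END", and again from baseline to the 3- and 6-month follow-ups. It then looks for the time of improvement "using delayed effect lags (one effect equals 1 day) until p-value 0.05 is reached". For actigraphy, besides a 2x2 time-by-group ANOVA, it states: "Rate of change in physical activity from BAS to END will also be examined using DD method".

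The randomised element that such a test can use is given in Section 3: the biostatistician will "create a randomization scheme to determine the number of days for the pre-treatment baseline period for each individual participant (2 weeks on average". Section 9.5.4 describes the series: "The Daily Diary will be administered for an average of 14 days during the initial baseline period through treatment".

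On the course of treatment, Section 3 gives sessions 1-5 to education, formulation and goals and says "Graded exposure begins in session 6". Section 5.1 has exposures presented in graded order, milder ones first.

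The diary hypotheses in Section 9.1 compare GET Living with TPM. The plan does not name the test statistic, the range of start days, the sidedness, a rule for pooling over patients, or how the arms are compared on the diary.

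**The concern.** The stated question is whether the diary differs between baseline and discharge. A randomization test takes its validity from what was randomised. Here that is the treatment start day, so the observed statistic is ranked against the values it would take at the other admissible start days. A patient can be much better at discharge without the true start day standing out from its neighbours.

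This matters because the documents describe a treatment that would be expected to act gradually and, for its exposure component, late. A treatment with early onset could look better on the diary than one that reaches the same discharge level slowly. A slope, which is what a rate of change in activity is, is not estimated by a level-shift test either. Section 2.1 says that the trial's findings are to support or refute a larger multi-site trial, so a misleading exploratory result could carry forward.

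**Working it through.** **No diary figure to reproduce.** The plan gives no power, effect size or SD for the diary test. Its questionnaire power statements do reproduce with a two-sample t-test at 29 per arm: 87.3% for fear (difference 17.4, SD 21; stated 87%) and 64.8% for disability (7, SD 11.2; stated 65%).

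**Inputs from the documents.** Mean baseline is 14 days. Treatment is "delivered twice a week over for up to 6 weeks" in Section 5.1, so 42 days; Section 3 says up to 12 weeks, and the two must be reconciled. Session 6 at two sessions a week falls 5 x 3.5 = 17.5 days after session 1. About 29-30 patients per arm are expected at the end of treatment or study.

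**Assumptions.** Statistic: treatment mean minus baseline mean, in the direction of improvement. Start day uniform on days 4-24 or 7-21. Daily SD 1, AR(1) 0.3, one-sided 0.05, improvement mainly 1-2 SD.

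**Step 1: smallest attainable p.** With K possible start days it is 1/K. Days 4-24 give 1/21 = 0.048. Days 7-21 give 1/15 = 0.067, so no single patient can reach 0.05 for any pattern. At least 20 start days are needed (1/20 = 0.05).

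**Step 2: why a ramp is missed, without noise.** Let the true start be after s baseline days, and let improvement rise linearly to D over 42 days.
- Candidate start c at or before s: difference = 21.5D/(s + 42 - c), which rises with c.
- Candidate k days after s: difference = D[43 + k(s - 1)/(s + k)]/84, which also rises with k.
- Example, s = 14: 0.439D at day 7, 0.512D at the true day 14, 0.563D at day 21.
- An immediate step with s = 14 gives 0.857D, 1.000D and 0.667D at those days, so the true start stands out.

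On days 7-21 with the ramp, true starts of 7, 14 and 21 rank 15th, 8th and 1st of 15. The true start ranks first only when it happens to be the last admissible day, whatever the size of D. On days 4-24 that has probability 1/21 = 4.8%. A ramp that begins about 17 days into treatment behaves the same way over this delay: the candidate baseline mean stays at zero while the treatment mean keeps rising.

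**Step 3: with noise, no lag.** Ranges are over separate simulations, windows and effect sizes.

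| Course | Single patient (days 4-24) | Pooled over 30 |
|---|---|---|
| No effect | 4-5% | 5-6% |
| Immediate step | 19-42% | 100% |
| Ramp complete in 14 days | 7-9% | 22-96% |
| Ramp over 42 days | 4-6% | 6-23% |
| Ramp from session 6 | about 4% | 1-6% |

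The 42-day pooled range includes an effect of 3 SD (23%). Allowing for simulation error, the two slow courses together span roughly 1-30%. Replacing the treatment mean by the last-7-day mean gave 17-24% and about 5% for them (pooled, 1.5 SD). A slope-change statistic gave roughly 25-48% for the 42-day ramp (60 replicates, so rough).

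**Step 4: the lag search, lags 0-18.** Single patient, days 4-24, 2 SD, proportion reaching 0.05 at some lag: no effect 57%, 42-day ramp 66%, ramp from session 6 40%. Pooled, 1.5 SD: no effect 27-35%, 42-day ramp 55-67%, ramp from session 6 11-17%. The late ramp is flagged less often than no effect at all.

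**Step 5: a between-arm comparison on the same diary days.** Last 7 treatment days minus baseline mean, 29 per arm, 42-day ramp. The TPM effect was set at 5/22.4 of the GET Living effect and the between-patient SD at 21/22.4 of it, the ratios in Section 9.2. Power was 71%, 78% and 84% for a GET Living effect of 1, 1.5 and 2 SD. This tests a different hypothesis (arm against arm), so it shows feasibility and is not a like-for-like gain.

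**The case against.** The strongest reply is that the plan leaves open the very items on which these figures depend. Another statistic or a wider window could do better, and the pooled slope-change result shows that it can. This stands, and it is why the size is given as conditional.

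A reader might infer that the test rejects only for an abrupt shift on the start day. The documents do not support that: under the same assumptions, a pooled test detects a 3-day ramp in 97-100%, a 7-day ramp in 48-100% and a 14-day ramp in 22-96%.

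A reader might also infer that patients who improve gradually would usually be reported as unchanged. That ignores the lag search in the next sentence of Section 9.1, under which about 66% of patients with a 42-day ramp reach 0.05 at some lag. The difficulty is that about 57% with no effect do so too.

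The time course is an expectation as well. Session 5 already includes a mini-exposure and plans home exposures (Table 2), and no document states that diary scores stay flat and then fall.

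Finally, the discharge question is answered elsewhere: fear and disability by mixed models, and activity by a 2x2 ANOVA. That limits the consequence. It does not supply the between-arm diary analysis that the Section 9.1 hypotheses call for.

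**Conclusion.** The concern holds in a limited form. With a phase-mean difference and no lag, the planned test is a poor answer to the baseline-to-discharge question when improvement is slow: about 4-6% power per patient and roughly 1-30% pooled. The lag search does not restore power at a controlled 5% level. The algebra in Step 2 does not depend on the noise model, but it does depend on that statistic and on a linear course. The percentages also rest on the assumed window, autocorrelation, effect sizes and pooling rule.

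The missing specification is a defect in its own right, since fewer than 20 start days would make a single-patient result at 0.05 impossible. Diary and actigraphy are exploratory, and nothing here affects the primary questionnaire analysis. The change is worth making because it is cheap and the diary hypotheses compare arms.

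**What to change.** In the Section 9.1 Aim 1 Analysis Plan:

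1. Make the baseline-to-discharge diary analysis a between-arm comparison of the last-7-treatment-day mean, adjusted for the patient's baseline-period mean. Use ANCOVA, or a mixed model of daily scores with time as weekly categories or a spline. A single linear slope would misfit a flat-then-falling course.
2. Use the same model on daily activity for the actigraphy rate-of-change sentence, alongside the planned 2x2 ANOVA.
3. Keep the single-case test only as a secondary per-patient description of abrupt onset. Name its statistic, start-day window and pooling rule, and state that a non-significant result is not evidence of no improvement by discharge.
4. Give the days-to-improvement hypothesis its own analysis. The changes above do not answer it.

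The cost is SAP wording and a little more analysis of data already collected, with no extra patients or visits. The downside is less direct comparability with the pilot's single-case results.
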